5.4 Exclusion Criteria

Subjects who present and/or self-report with the following criteria will not be eligible to participate in the study:

Smoking Behavior

1. Use of less than 10 cigarillos in lifetime.
2. Current enrollment or plans to enroll in a tobacco cessation program over the duration of the study.
3. Current use of nicotine replacement therapy or other smoking cessation medication.

Alcohol and Drug

1. History of substance abuse (other than nicotine dependence) in the past 12 months and/or currently receiving medical treatment for substance abuse. Counseling and support groups (e.g., Alcoholics Anonymous and Narcotics Anonymous) will not be considered medical treatment for the purposes of this protocol.
2. Current alcohol consumption that exceeds 25 standard drinks/week.
3. Breath alcohol reading (BrAC) greater than .000 at Laboratory Visit 1.
4. Use of e-cigarettes on > 15 days in the past 30 days.

Medical

1. Women, including all individuals assigned as “female” at birth, who are pregnant, breast feeding, or planning a pregnancy over the duration of the study period.
2. Serious or unstable disease within the past year (e.g., cancer, heart disease). Applicable conditions will be evaluated on a case-by-case basis by the Principal Investigator.

Psychiatric

1. Lifetime history of schizophrenia or psychosis.
2. Lifetime history of suicide attempt(s) requiring intervention AND recurring suicidal thoughts or ideations. Evaluated on a case-by-case basis by the Principal Investigator.
3. Current or recent use of anti-psychotic medications.

General Exclusion

1. Past, current, anticipated, or pending enrollment in another research program over the study period that could potentially impact subject safety, study data, and/or the study design as determined by the Principal Investigator.
2. Any medical condition, illness, disorder, adverse event (AE), or concomitant medication that could compromise participant safety or significantly impact study performance as determined by the Principal Investigator. Subjects may be deemed ineligible for any of

CONFIDENTIAL

This material is the property of the University of Pennsylvania. Do not disclose or use except as authorized in writing by the study sponsor

the aforementioned reasons at any point throughout the study, as well as during the initial telephone screen.

3. Significant non-compliance with protocol and/or study design as determined by the Principal Investigator. Subjects may be deemed ineligible at any point throughout the study.

5.5 Vulnerable Populations

Children, pregnant women, fetuses, neonates, or prisoners are not included in this research study. Educationally or economically disadvantaged persons are included but not solely targeted for recruitment. Because of our recruitment efforts for this study, it is possible that University of Pennsylvania employees and students may be invited to participate. Status of participation in the current study will be independent of the participant's work or school activities.

5.6 Subject Recruitment

Participants may be recruited from print, traditional, and social media advertisements, referrals, and/or from our database of previous participants who have agreed to be re-contacted for future studies. All advertising materials will be submitted to the UPENN IRB for approval prior to distribution/posting. Interested participants will first complete a telephone screen to assess their initial eligibility. Participants who are initially eligible will be screened against our registration database to confirm that they are not currently participating in another research study at our Center and have not previously reported a condition or circumstance that would make them ineligible for the current study. These participants who remain initially eligible will then be invited to attend Laboratory Visit 1 at our Center during which they will be presented with the IRB-approved combined informed consent and HIPAA Form and have their final eligibility confirmed. Initially eligible participants will also have the option to review and sign the combined informed consent and HIPAA Form electronically via REDCap prior to completing the rest of Laboratory Visit 1 at our Center.

5.7 Early Withdrawal of Subjects

5.7.1 When and How to Withdraw Subjects

Participants are free to withdraw from the study on their own accord at any time. In addition, participants may be withdrawn by the Principal Investigator at any time per the exclusion criteria listed previously. No follow-up data collection is required for participants who withdraw or are deemed ineligible throughout the study.

6. Study-Provided Cigarillos

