7.5 Analytic Plan

Prior to analyses, standard data cleaning, assumption evaluation, and imputation methodology will be applied. We conservatively assume that 85% of our participants will complete all study visits, and will recruit additional subjects (15%, 13) to replace those who fail to return. The baseline characteristics of subjects who drop out will be examined, with attention to whether there is an association between dropout and flavor preference. Female sex and race will be included in each model. We will also consider baseline variables potentially important to flavor preference (e.g., cigarette smoking status, menthol brand, cigarillo history, prior flavor preference, blunt use, depression, sensation-seeking, cigarillo flavor risk beliefs, and exposure to cigarillo flavor marketing) for inclusion in the multivariate models if bivariate associations with the outcome are $p \leq .20$. Outcomes will be analyzed using general linear models (GLM) with outcome family and links appropriate to each of the respective measures. Where measures are repeated, GLMs will be fitted with generalized estimating equations (GEE).

Aim 1 H1 will determine whether the subjective rewarding value of a sweet flavored cigarillo is greater than that of a non-flavored cigarillo among young adults. H1 will test whether participants report greater subjective rewarding value from a sweet flavored cigarillo than a non-flavored cigarillo. The outcome measure used for analysis is a continuous subjective rating of reward for sweet flavored and non-flavored cigarillos obtained at the first exposure (visit 1). The analysis will use a paired t-test (or GLM equivalent) to assess the effect of flavor. Female sex and race will be included in the model.

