Reproductive Risks: Smoking can cause serious harm to unborn children or children who are breast-feeding. Female participants are asked to use a medically accepted method of birth control (such as IUD, birth control pills, condoms, etc.) while participating in the study. Further, female participants, and those assigned as female at birth, will be asked to administer a simple, one-step hCG pregnancy test and informed that if they are (or believe they may be) pregnant that they will not be eligible to participate in the research study. If a female participant becomes pregnant over the course of the trial, they will be immediately withdrawn. It will also be recommended that the participant seek consult from an obstetrician or maternal-fetal specialist about the dangers of smoking while pregnant.

Assessments: Some participants may experience some emotional distress during the assessments due to learning their carbon monoxide levels or seeing how many cigarillos they smoke. These events happen very rarely and in almost all cases are short-lived and of low intensity. If a participant does exhibit a high level of emotional distress, however, they will be offered contact information for mental health services in the area.

CONFIDENTIAL

This material is the property of the University of Pennsylvania. Do not disclose or use except as authorized in writing by the study sponsor

Email Communications: In this research study participants may prefer to receive appointment reminders via email or submit questions related participation via email. Email is not a secure means of communication. Email messages travel across the Internet passing through multiple computers before reaching their final destination. It is not possible to know whether an email a participant sends will be viewed along the way. Additionally, if sent messages are not deleted, an email provider may have an archive of everything that is sent. If someone gets access to an email account (for example, a participant's family member), they could see archived messages. There are many other ways in which emails are not secure—these are only selected examples. To manage this risk the informed consent form will include specific language to educate research participants on the privacy risks involved in email communications. Participants will also be explicitly instructed to only use email communications for routine matters and never for personal or confidential messages or questions.

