9.1 Definitions

Unanticipated Problems Involving Risk to Subjects or Others:

Any incident, experience, or outcome that meets all of the following criteria:

- Unexpected in nature, severity, or frequency (i.e. not described in study-related documents such as the IRB-approved protocol or consent form, the investigators brochure, etc.)

CONFIDENTIAL

This material is the property of the University of Pennsylvania. Do not disclose or use except as authorized in writing by the study sponsor

- Related or possibly related to participation in the research (i.e. possibly related means there is a reasonable possibility that the incident, experience, or outcome may have been caused by the procedures involved in the research)
- Suggests that the research places subjects or others at greater risk of harm (including physical, psychological, economic, or social harm).

Adverse Event:

An **adverse event** (AE) is any symptom, sign, illness or experience that develops or worsens in severity during the course of the study (regardless if study-related). Intercurrent illnesses or injuries should be regarded as adverse events. Abnormal results of diagnostic procedures are considered to be adverse events if the abnormality:

- results in study withdrawal
- is associated with a serious adverse event
- is associated with clinical signs or symptoms
- leads to additional treatment or to further diagnostic tests
- is considered by the investigator to be of clinical significance

Serious Adverse Event:

Adverse events are classified as serious or non-serious. A **serious adverse event** (SAE) is any AE that is:

- fatal
- life-threatening
- requires or prolongs hospital stay
- results in persistent or significant disability or incapacity
- a congenital anomaly or birth defect
- an important medical event

Important medical events are those that may not be immediately life threatening, but are clearly of major clinical significance. They may jeopardize the subject, and may require intervention to prevent one of the other serious outcomes noted above. For example, drug overdose or abuse, a seizure that did not result in in-patient hospitalization, or intensive treatment of bronchospasm in an emergency department would typically be considered serious.

All adverse events that do not meet any of the criteria for serious should be regarded as **non-serious adverse events**.

Adverse Event Reporting Period:

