The study period during which AEs/SAEs will be reported is from the initiation of any study procedures until the end of the study. Any event(s) that the subject, or the subject's personal physician, believes might reasonably be related to participation in the study after the final time point will be assessed and reported as appropriate.

Preexisting Condition:

A preexisting condition is one that is present at the start of the study. A preexisting condition should be recorded as an adverse event if the frequency, intensity, or the character of the condition worsens during the study period.

Post-study Adverse Event:

All unresolved adverse events should be followed by the investigator until the events are resolved, the subject is lost to follow-up, or the adverse event is otherwise explained. At the last scheduled visit, the investigator should instruct each subject to report any subsequent event(s) that the subject, or the subject's personal physician, believes might reasonably be related to participation in this study.

CONFIDENTIAL

This material is the property of the University of Pennsylvania. Do not disclose or use except as authorized in writing by the study sponsor

Hospitalization, Prolonged Hospitalization or Surgery:

Any AE that results in hospitalization or prolonged hospitalization should be documented and reported as a SAE unless specifically instructed otherwise in this protocol. Any condition responsible for surgery should be documented as an AE if the condition meets the criteria for an AE.

Neither the condition, hospitalization, prolonged hospitalization, nor surgery are reported as an adverse event in the following circumstances:

- Hospitalization or prolonged hospitalization for diagnostic or elective surgical procedures for a preexisting condition. Surgery should **not** be reported as an outcome of an adverse event if the purpose of the surgery was elective or diagnostic and the outcome was uneventful.
- Hospitalization or prolonged hospitalization required to allow efficacy measurement for the study.
- Hospitalization or prolonged hospitalization for therapy of the target disease of the study, unless it is a worsening or increase in frequency of hospital admissions as judged by the clinical investigator.

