9.2 Collection and Recording of Adverse Events

9.2.1 AE Collection Methods

All AEs and SAEs occurring during the study period will be captured through the methods described below:

1. Open-Ended AE Form: Participants will be asked an open-ended question about any symptom or medical event that may be related to their study participation. These events will be documented as **unanticipated (unexpected)** AEs unless they are otherwise outlined in the protocol or consent (i.e. related to withdrawal, assessments, etc.). The reporting period for each assessment will inquire about any event(s) or symptom(s) experienced since the last in-person visit. If a participant reports a symptom or medical event, they will be asked to rate the severity of the event utilizing the following severity scale: 0 (None=No Concerns), 1 (Mild=Issue does not interfere with usual daily activities), 2 (Moderate=Issue does interfere with some activities), and 3 (Severe=No normal activities are possible). Any report on the Open-Ended AE Form will require additional follow up per the AE documentation and internal reporting procedures outlined below in section 8.2.2.
2. Spontaneous Assessment: Once enrolled, participants will be instructed to inform the research team about any notable symptom or medical event/concern throughout their participation in the study. A participant may also request the Principal Investigator be consulted about any reported medical event or concern of any severity at any time throughout their participation.
3. An “AE Note” template will be available to the research staff to collect supporting AE information and will function as the source document. However, research staff may collect AE information on any source document available to them and transfer the relevant information to a formal AE Note at a later time. Any notable AE reported spontaneously will require additional follow up per the AE documentation and internal reporting procedures outlined below in section 8.2.2.

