 - Unlikely = Doubtfully related
 - Possibly = May be related
 - Probably = Likely related
 - Definitely = Related
- Clinical assessment of subject conducted at time of SAE (if appropriate)
- Results of any laboratory tests and/or diagnostic procedures (if appropriate)
- Autopsy findings (if appropriate)
- Concomitant medications and therapies (excluding treatment of event)
- Relevant Medical History (if appropriate)

Internal Reporting Procedures: All relevant follow-up information outlined above (see AE/SAE documentation) concerning applicable AEs, including all information regarding the occurrence of previously reported event(s), will be reported to the Study Coordinator (or other senior personnel) and Principal Investigator to determine a course of action (e.g. continue to monitor), relatedness (causality) to the study, and expectedness (if not already established). This consult will be documented via email. The clinical course of each event will be followed until resolution, stabilization, or until it has been determined that the study treatment or participation is not (or unlikely) to be the cause.

SAEs that are still ongoing at the end of the study period must be followed up to determine the final outcome unless it has been determined that the study treatment or participation is not the cause. Any SAE that occurs after the study period and is considered to be possibly related to the study treatment or study participation should be recorded and reported immediately per this protocol.

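### Section 5.7.1 waives follow-up after withdrawal with no safety exception, unreconciled with 9.1 and 9.2.2; separately, no scheduled adverse-event query covers anyone's last smoking session, and non-completers also miss the exit instruction

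*Combined protocol and SAP*

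**What the plan says.** **Leaving the study.** Section 5.7.1 lets participants withdraw at any time and lets the investigator withdraw them under the exclusion criteria. It then says: "No follow-up data collection is required for participants who withdraw or are deemed ineligible throughout the study". It does not mention adverse events or refer to Section 9. Section 5.4 (General Exclusion, item 2) includes an adverse event among the reasons for which someone may become ineligible at any point in the study.

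**Following known events.** Section 9.1 (Post-study Adverse Event) says: "All unresolved adverse events should be followed by the investigator until the events are resolved, the subject is lost to follow-up", or the event is otherwise explained. Section 9.2.2 says: "The clinical course of each event will be followed until resolution, stabilization", or until the study is judged not, or unlikely, to be the cause. Neither section exempts participants who have left.

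**Detecting new events.** Section 9.2.1 says of the open-ended form: "The reporting period for each assessment will inquire about any event(s) or symptom(s) experienced since the last in-person visit". It also tells enrolled participants to report notable symptoms on their own initiative. Section 9.1 adds an instruction, given at the last scheduled visit, to report later events believed to be related to the study.

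**Expected attrition.** Section 7.5 says: "We conservatively assume that 85% of our participants will complete all study visits". It plans 13 (15%) extra recruits to replace those who do not come back. Section 5.2 plans 100 recruits for 86 with complete data.

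**The concern.** There are two distinct issues, and neither causes the other.

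The first is the handling of a known event. A person removed because of an adverse event falls under 5.7.1, which asks for nothing further, and under 9.1 and 9.2.2, which ask for follow-up. Staff working from 5.7.1 alone could close the record while the event is still open.

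The second is the detection of an event nobody has yet reported. The effects of a smoking session are asked about only at the next visit, so a participant who does not return is not asked about the last session attended. Section 8.1 names nausea, dizziness and rapid heartbeat as possible effects of the cigarillos, and these are plausible reasons for not coming back. The dropout analysis in 7.5 looks at baseline characteristics, with attention to flavor preference. It would not show whether symptoms led people to leave.

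What is at stake is the completeness of the safety record and the care of a few participants. The three efficacy comparisons are not involved.

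**Working it through.** **1. The plan's attrition figure.** Inputs are the 86 completers and 85% completion (7.5) and the 100 recruits (5.2).

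- 0.15 × 86 = 12.9, which rounds to 13. This reproduces the figure in 7.5.
- 100 − 86 = 14, from 5.2.
- 0.15 × 100 = 15, applying 15% to the recruitment target.
- 86 / 0.85 = 101.2, so 102 recruits, and 0.15 × 102 = 15.3.

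The expected number of non-completers is therefore about 13 to 15. Section 7.5 describes them as people who fail to return, so most should have attended Visit 1 and smoked there. Anyone found ineligible at Visit 1 before smoking has no session to ask about.

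**2. Order of the form and the smoking session (7.2.2 to 7.2.4).**

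| Visit | Adverse-event form | Smoking | Form first? |
|---|---|---|---|
| 1 | step 11a | step 12 | yes |
| 2 | step 6 | step 9 | yes |
| 3 | step 6 | step 7 | yes |

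**3. Sessions covered by a later form.** The form looks back to the last in-person visit, so a session is covered only if another visit follows.

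| Participant | Sessions | Covered later | Not covered |
|---|---|---|---|
| Leaves after Visit 1 | 1 | 0 | Visit 1 (6 puffs) |
| Leaves after Visit 2 | 2 | 1 | Visit 2 (10 puffs) |
| Completes | 3 | 2 | Visit 3 (90 minutes, ad libitum) |

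In every row the uncovered session is the last one. The detection gap therefore applies to everyone who smokes. It comes from the form order and the look-back window, and it would exist whatever 5.7.1 said.

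**4. How non-completers differ.** A completer attends the last scheduled visit and receives the 9.1 instruction to report later events. Someone who fails to return after Visit 1 or 2 does not. That person has the general instruction in 9.2.1 and the chance to tell staff of symptoms while on site (8.1).

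**5. The follow-up rules side by side.** Section 5.7.1 says follow-up data are not required. Sections 9.1 and 9.2.2 say open events should be, or will be, followed. The listed stopping points are resolution, stabilization, loss to follow-up, another explanation, or a judgment that the study is not or unlikely to be the cause. Withdrawal is not among them. The text does not say which rule governs someone who leaves with an open event.

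**The case against.** The strongest reply is that 5.7.1 only declines to require data and does not bar collection. The specific safety duties in 9.1 and 9.2.2 can then be read alongside it, leaving a gap in clarity. That stands as far as it goes. A reader might infer that 5.7.1 ends all collection, or that every event must be followed to resolution, and the text supports neither. The gap still needs closing, because 5.4 and 5.7.1 together put a participant removed for an adverse event under both rules.

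It can also be said that existing safeguards cover much of the detection risk. Participants are told from enrollment to report notable symptoms. Section 8.1 describes the expected symptoms as typically mild and short-lived. The Visit 1 exposures are 20 minutes apart, and Visit 2 ends with a one-hour wait, so many acute effects would appear on site. This is fair and lowers the stakes. However, no adverse-event question is scheduled in those intervals, so detection depends on the participant speaking up.

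Finally, a reader might infer that the missing query is peculiar to the 15% who leave, or that it results from 5.7.1. Step 3 of the working shows otherwise: completers' Visit 3 session is also unqueried, and the cause is the form order.

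**Conclusion.** Both points hold, at minor weight. Sections 5.7.1, 9.1 and 9.2.2 must be reconciled for a participant who leaves with an open event. Separately, no scheduled query covers anyone's last smoking session. About 13 to 15 expected non-completers, where they smoked at least once, also miss the last-visit instruction. The count rests on the protocol's own 85% completion assumption and on most non-completers having smoked at Visit 1.

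Three further inferences are not supported:

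- **A size for the bias in the adverse-event rate.** The documents give no symptom rate and no link between symptoms and leaving, so no figure can be put on it. Under-recording is plausible, but its amount is unknown.
- **That a low recorded rate underwrites the minimal-risk statements.** Those statements in 8.1 and 8.3 are judgments made before the study. They are not estimates from its data.
- **That withdrawal for pregnancy shows the conflict.** Section 9.1 does not itself list pregnancy as an adverse event, so such a withdrawal does not by itself leave an open event to follow.

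The primary outcomes in 7.4.3 are reward and reinforcement measures and are unaffected.

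**What to change.** **Section 5.7.1.** Limit the waiver to outcome data, for example: *No further outcome data are required; safety follow-up under 9.1 and 9.2.2 still applies.*

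**One brief phone contact.** Make it when a participant who has smoked any study cigarillo withdraws, is withdrawn or does not return, and only if the participant is willing. The call would:

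- ask the existing open-ended adverse-event question for the period since the last session;
- record the reason for leaving, which the dropout analysis in 7.5 now lacks;
- give the 9.1 instruction to report later events.

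Use the phone, which is already a reminder channel under 7.2.1. Email is unsuitable because 8.1 tells participants to keep it to routine matters.

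**Cost.** A short amendment and about 15 short calls by existing staff. Some people will not be reachable, and 9.1 already accepts loss to follow-up as a stopping point. Visits, exposures and outcome analyses do not change.

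**Limit.** This contact does not cover the Visit 3 session of the 86 completers. That gap has to be handled separately.
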